6.6 HANDLING OF MISSING DATA AND OUTLIERS

Section 7.3 of the CTP describes the handling of missing data.

Date: 07-08-2024, Version 1.0

Missing or incomplete AE dates are imputed according to BI standards (9.1). Missing data and outliers of PK data are handled according to BI standards (9.2).

For incomplete information on the date of first diagnosis, time since first diagnosis will be calculated as follows:

- If the year of first diagnosis is unknown, time since first diagnosis will be set to missing.
- If day and month of the first diagnosis are unknown, time since first diagnosis will be calculated as if diagnosed on the 30th June of that year.

c43421787-01

Proprietary confidential information © 2024 Boehringer Ingelheim International GmbH or one or more of its affiliated companies.

• If only the day of the first diagnosis is unknown, time since first diagnosis will be calculated as if diagnosed on the 15th of that month.

6.7 BASELINE, TIME WINDOWS AND CALCULATED VISITS

Unless otherwise specified, measurements reported with date and time and taken prior to start of administration of trial treatment will be considered pre-treatment values; measurements reported with a date only (and no time) and taken on the day of first administration of trial treatment will also be considered pre-treatment values. These pre-treatment values will be assigned to visits according to the nominal visit number as recorded on the eCRF or as provided by the laboratory.

Patient reported output (PRO) measurements reported prior to/on the date of the drug administration will be taken as pre-treatment values, regardless the time of measurements taken if there exist.

Baseline, unless otherwise specified, is defined as the last measurement collected prior to the start of administration of the trial treatment.

Measurements taken after start of administration of trial treatment will be considered either on- or off-treatment values based on the definition in Section 6.1, and will be assigned to visits for statistical analysis, if applicable, as defined below.

[figure not shown]
Analysis of AE data, potentially clinically significant abnormal laboratory values, concomitant medication or non-drug therapies, as well as use of rescue medication will not be based on visits. Frequency tables for these data will be using on-treatment data and categorized based on their occurring/starting dates. Therefore, no assignment to time windows will be necessary for such data.

The derivation of the last value, minimum value and maximum value of laboratory and vital signs data will consider all on-treatment values (whether or not selected in any time window; see Table 6.1: 1 for definition of the on-treatment period) within the period of interest; these will be derived for analysis of laboratory and vital signs data.

All other safety, efficacy and biomarker measurements will be assigned to visits based on extended time windows around the planned visit dates, defined relative to the day of first trial treatment (which is scheduled for Visit 2). These extended time windows are defined in Table 6.7: 1 and Table 6.7: 2.

c43421787-01

c43421787-01

c43421787-01

Proprietary confidential information © 2024 Boehringer Ingelheim International GmbH or one or more of its affiliated companies.

7. PLANNED ANALYSIS

The primary objective for dose finding Phase IIb (Part 1) are as follows:

- (1) to demonstrate a non-flat dose response curve, evaluate the quantitative treatment effect size, and evaluate the dose-response relationship based on the primary endpoint of percent change from baseline in dT count at Week 8;
- (2) to determine an optimal dose candidate for Part 2 by incorporating information of available safety and of efficacy based on the primary endpoint of percent change from baseline in dT count at Week 8.

The primary and interim analysis for Part 1 will be conducted after the last trial participant completes the Week 8 visit and Week 16 visit respectively. Final trial analysis is planned to be performed at the end of the study once all randomized patients have completed the study (including any follow-up period). If applicable, details of biomarker analyses will be provided in a separate Biomarker Statistical Analysis Plan.

For End-Of-Text (EoT) tables, the set of summary statistics is: N / Mean / SD / Min / Median / Max.

For tables that are provided for endpoints with some extreme data, median, quartiles and percentiles should be preferred to mean, standard deviation, minimum and maximum.

Tabulations of frequencies for categorical data will include all possible categories and will display the number of observations in a category as well as the percentage (%) relative to the respective treatment group (unless otherwise specified, all subjects in the respective subject set regardless of whether they have non-missing values or not).

The precision for percentages should be one decimal point, unless the denominator is smaller than 100 (in all treatment columns), in which case percentages are given in integer numbers. The category missing will be displayed only if there are actually missing values.

7.1 DEMOGRAPHIC AND OTHER BASELINE CHARACTERISTICS

Only descriptive statistics are planned for this section of the report.

Date: 07-08-2024, Version 1.0

Descriptive statistics will be presented by treatment for demographic variables and baseline characteristics, based on the FAS. More details could refer to Section 5.4.1.

For continuous demographic variables listed in Table 7.1:1, they will be presented by the number and percentage of patients in the categories defined in Table 7.1:1.

Proprietary confidential information © 2024 Boehringer Ingelheim International GmbH or one or more of its affiliated companies.

Table 7.1: 1 Categories for demographic variables and baseline characteristics

·	
Variable	Categories
Age	< 30 years 30 to < 65 years ≥ 65 years
Weight	≤60 kg >60 to ≤90 kg >90 kg
Weight based on popPK model #	<72kg 72 to ≤122kg >122kg
BMI	< 25 kg/m2 25 to < 30 kg/m2 ≥ 30 kg/m2
Time since first diagnosis	 ≤ 1 year > 1 to ≤ 5 year > 5 to ≤ 10 years > 10 years
Baseline dT count	
Neutrophil level	High > 7.23 X10^9 /L Low ≤ 7.23 X10^9 /L
Baseline neutrophil/lymphocyte ratio	1 to <=2 >2 to <=3 >3
IHS4 severity	Mild: ≤ 3 Moderate: >3 to ≤ 10 Severe: >10

[#] The cut-off values of weight are based on the body weight values corresponding to the range of 80% to 125% of steady-state AUC0- τ (any dosing regimen) using 94 kg as a reference, according to the population PK model.

7.2 CONCOMITANT DISEASES AND MEDICATION

Date: 07-08-2024, Version 1.0

Only descriptive statistics are planned for this section of the report.

Concomitant diseases (i.e., baseline conditions) and concomitant non-drug therapies will be coded according to the most recent version of Medical Dictionary for Drug Regulatory Activities (MedDRA). Concomitant medications will be coded according to the most recent version of the World Health Organization – Drug Dictionary (WHO-DD).

Proprietary confidential information © 2024 Boehringer Ingelheim International GmbH or one or more of its affiliated companies.

Concomitant diseases which are present at start of the study will be descriptively summarized by treatment based on the FAS.

A medication/non-drug therapy will be considered concomitant to treatment, if it

- Is ongoing at the start of first study dose or
- Starts within the on-treatment period (see Section 6.1 for the definition)

A medication/non-drug therapy will be considered as prior medication/non-drug therapy, if the end date of the medication/therapy is at any time prior to the start of first study dose.

Concomitant medication use (excluding rescue medication) taken at any time during the ontreatment period (cf. Section 6.1) will be summarized by treatment based on FAS, with frequency and percentage of patients by Anatomical Therapeutic Chemical 3 (ATC3) class and preferred name.

Concomitant use of non-drug therapies (excluding rescue therapy) taken any time during the on-treatment period (cf. Section 6.1) will be summarized by treatment based on FAS, with frequency and percentage of patients.

Use of rescue medication will be summarized separately based on FAS.

7.3 TREATMENT COMPLIANCE

Only descriptive statistics are planned for this section of the report. Treatment compliance (see Section 5.4.2 for the definition and calculation) will be summarized by treatment and period on SAF using descriptive statistics (N, mean, SD, minimum, median, maximum).

7.4 PRIMARY OBJECTIVE ANALYSIS

7.4.1 Main analysis

Part 1 (Phase IIb)

Date: 07-08-2024, Version 1.0

The main analysis of the primary endpoint will use a treatment policy estimand. Details of handling the intercurrent events are addressed in Section 7.2.2 of the clinical trial protocol and Table 6.3.1. This main analysis of the primary efficacy endpoint will be performed on the full analysis set. Subjects will be analyzed according to the stratum to which they actually belong. Missing data will be handled using a mixed effects model with repeated measures (MMRM) under the assumption of missing at random.

The descriptions below are based on the primary objective and secondary objective, respectively.

Proprietary confidential information © 2024 Boehringer Ingelheim International GmbH or one or more of its affiliated companies.

Primary Objective: Dose Finding

For the primary endpoint analysis, first a mixed effect model for repeated measurements (MMRM) is calculated to estimate the treatment effects and the corresponding covariance matrix. Using the MCPMod approach (9.4, 9.5), these estimates are then further used to

- (1) test for a non-flat dose response curve
- (2) identify suitable dose-response shapes out of a selection of candidate models.

The final dose-response model is derived as a weighted average over all significant model shapes. Planned total dose before Week 8 will be used to evaluate dose response curve.

Details on both the specification of the MMRM and the MCPMod approach are given in the CTP Section 7.2.2.

MMRM analysis

The % change in dT count from baseline (Visit 2), at Visits 4, 6, 8 and 10 (, 8) will be evaluated using an MMRM accounting for the following sources of variation: fixed, categorical effects of treatment at each visit, TNFi status at baseline and categorical baseline dT count at each visit. The unstructured covariance structure will be used to model the within patient measurements. To estimate denominator degrees of freedom the Kenward-Roger approximation will be used.

SAS code for MMRM for the endpoint of dT count:

PROC MIXED DATA=alldat cl method=reml;

CLASS dt_base_categorical visit trt TNFi subject;

MODEL ept = TNFi visit*trt dt_base_categorical *visit/ddfm=kr s CL;

REPEATED visit / subject= subject type=un r rcorr;

LSMEANS visit*trt / pdiff=all om cl alpha=0.05 slice=visit;

RUN;

Results of the MMRM (N, mean, SE and 95% CI per dose group and timepoint) will be presented in tables and displayed graphically.

MCPMod Analysis

Date: 07-08-2024, Version 1.0

For the primary analysis the dose-response relationship will be modeled using the total doses. Here, the total is the sum of all doses administered to the patient prior to the week 8 visit including both loading and maintenance phase. Thereby, it is assumed that the cumulative concentrations over time (AUC) and thus the cumulative total dose is the key driver of the efficacy response in the modelling part of MCPMod. Table 7.4: 1 shows the calculated total doses per treatment arm.

Proprietary confidential information © 2024 Boehringer Ingelheim International GmbH or one or more of its affiliated companies.

Table 7.4: 1 Total dose per treatment arm

Treatment arm	Total dose
High dose regimen (Arm 1)	
	Total dose: Spesolimab
Medium dose regimen (Arm 2)	
	Total dose: Spesolimab
Low dose regimen (Arm 3)	
	Total dose: Spesolimab
Placebo (Arm 4)	Placebo at
	Total dose: 0 mg Spesolimab

W: Week.

The multiple comparison procedure will then be implemented using optimal contrast tests, which control the family-wise type I error rate at a one-sided $\alpha = 0.05$. The optimal contrasts corresponding to each candidate model in the trial design stage are shown in Table 7.4: 2.

Table 7.4: 2 Contrast coefficients

Date: 07-08-2024, Version 1.0

	Contrast coefficients for (total) dose					
Model	Placebo	Low dose:	Medium dose: BI	High dose:		
Linear	0.592	0.254	-0.085	-0.761		
Exponential	0.458	0.304	0.071	-0.832		
Emax	0.820	-0.037	-0.293	-0.490		
SigEmax	0.641	0.302	-0.307	-0.635		
BetaMod	0.664	0.214	-0.692	-0.185		

BI: Spesolimab total dose, i.e., sum of all loading and maintenance doses administered before week 8

For the final evaluation, these contrasts will be updated using the expected model means from the candidate set and the estimated variance-covariance matrix extracted from the MMRM model. The final contrasts will be presented in the CTR.

A non-flat dose response curve is established if at least one dose-response model is statistically significant, i.e., rejecting the null hypothesis of a flat dose-response curve

Proprietary confidential information © 2024 Boehringer Ingelheim International GmbH or one or more of its affiliated companies.

indicates a benefit of spesolimab over placebo. If a non-flat dose response is established, the statistically significant models from the above candidate set are refitted to the data without any parameter assumptions to generate new estimates for all model parameters.

The final model is derived as a weighted average over all significant model shapes. Here, the weights for each significant model (M_k) are given by

$$w(M_k) = \frac{\exp(0.5 \cdot \operatorname{AIC}(M_k))}{\sum_{i=1}^k \exp(0.5 \cdot \operatorname{AIC}(M_i))},$$

Where $AIC(M_k)$ is the Akaike Information Criterion (AIC) of model M_k .

Estimates for each dose group will be calculated and final dose-response curve will be based on the final model. The confidence band for the final model will be based on parametric bootstrap approach by sampling from the multivariate normal distribution underlying the MMRM estimates and then fitting each of the models to each of these samples.

[figure not shown]
R code to perform the evaluations is available in Section 10.3.

The following displays are planned:

- Table of the updated contrast coefficients per dose group and candidate model, together with the MCPMod test statistics and p-values for each model and the critical value.
- For averaging model, figure of the dose-response curve and 95% confidence band for the bootstrap sampling.
- For all significant model shapes, figures of the dose-response curve plus 95% confidence band (of the predicated shape) and 95% CI per dose (estimated from MMRM).

c43421787-01

Proprietary confidential information © 2024 Boehringer Ingelheim International GmbH or one or more of its affiliated companies.

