# 7.2.3 Primary objective analyses

# Part 1 (Phase IIb) The primary endpoint for Phase IIb is percent change from baseline in dT count at The primary analysis consists of a of quantitative treatment benefit. is used to evaluate several possible dose response models (patterns), and to identify the best-fitting model or subset of models. To account for the repeated nature of the data and the covariates in the model,

will be carried out in SAS and covariate adjusted fixed effect estimates of average

c40061625-02 **Clinical Trial Protocol** Page 108 of 177 Proprietary confidential information © 2023 Boehringer Ingelheim International GmbH or one or more of its affiliated companies

response for each dose group and the covariance matrix will be extracted from the fit and used for Percent change from baseline in dT count will be used as the response variable in the will include fixed categorical effects of treatment at each visit, The status at baseline, and categorical baseline dT count at each visit. Visit will be treated as the repeated measure with an unstructured covariance structure used to model the within-trial participant measurements. The placebo effect in percent change from baseline in dT count at is assumed to be -10%, and the maximum effect in percent change from baseline in dT count at the investigated dose range relative to placebo is assumed to be -30%. The following model assumptions and resulting graphs (Figure 7.2.3: 1) have been selected for both plausible and a diverse range of dose response patterns. Planned total dose before will be used to evaluate dose response curve. Linear Exponential: Emax: SigEmax: BetaMod:

c40061625-02 Clinical Trial Protocol Page 109 of 177

Proprietary confidential information © 2023 Boehringer Ingelheim International GmbH or one or more of its affiliated companies

The optimal contrasts corresponding to the candidate models will be shown in the TSAP. For the final evaluation these contrasts will be updated using the estimated means for each dose group and the estimated variance-covariance matrix extracted from the primary analysis model.

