A non-flat dose response is established if at least one dose response pattern is statistically significant, rejecting the null hypothesis of a flat dose response relationship over percent change from baseline in dT count at jointly for each of the candidate dose response models with a contrast test controlled for the family-wise type I error rate at 1-sided  $\alpha$  of 0.05.

If non-flat dose-response is established, the statistically significant (best fitting) model(s) from the above candidate set are refitted to the data to generate new estimates for all model parameters. If more than one model is significant, the weighted average model will be evaluated to identify the for Part 2 for Pa

In addition to the results from \_\_\_\_\_\_ a beneficial treatment effect relative to placebo will be evaluated.

Baseline is defined as the last available data collected at Visit 2 prior to administration of first dose of study medication, or last available screening data if Visit 2 data are missing.

Page 110 of 177

Proprietary confidential information © 2023 Boehringer Ingelheim International GmbH or one or more of its affiliated companies

The primary analysis will be performed using the TS, as defined in Section 7.2.1. All available data from the TS in each active treatment arm and the placebo arm up to Week 8 will be used. Trial participants will be analysed according to the stratum to which they belong (regardless of any mis-assignment to treatment based on identification of the wrong stratum), as such an error occurs before randomisation and is therefore consistent with regulatory guidance.

In the primary analysis intercurrent events are handled with treatment policy approach, except for death (unexpected), see Section 7.2.2.

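### The model-averaging weight printed in SAP 7.4.1 has the wrong sign on AIC, so the significant model with the highest AIC gets the most weight

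*SAP*

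**What the plan says.** The MCPMod part of SAP 7.4.1 first tests the candidate shapes (linear, exponential, Emax, SigEmax, BetaMod). It then refits the significant ones with all parameters free and averages them. The section states the averaging twice: "The final dose-response model is derived as a weighted average over all significant model shapes", and later "The final model is derived as a weighted average over all significant model shapes. Here, the weights for each significant model", which leads into the weight formula.

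In plain notation the printed formula is w(M_k) = exp(0.5·AIC(M_k)) / Σ exp(0.5·AIC(M_i)), with i running from 1 to k. The exponent is positive above and below the line. The only definition beneath it says that the symbol "is the Akaike Information Criterion (AIC) of model" M_k. No formula for AIC is given, and nothing says its sign is reversed.

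The averaged model supplies the dose-group estimates and the final curve. The section closes the method with "R code to perform the evaluations is available in Section 10.3"; that section is not shown in the public text.

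Protocol 7.2.3 (Part 1) describes the modelling as a means "to identify the best-fitting model or subset of models". On averaging it says "If more than one model is significant, the weighted average model will be evaluated to identify", and its visible text gives no weight formula.

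**The concern.** With the usual definition, AIC = −2 log L + 2p, a lower value means better support, and Akaike weights use exp(−0.5·AIC). The printed formula reverses this. A model gains weight by fitting worse or by carrying more parameters, so the average leans towards whichever significant shape the data support least once complexity is counted. That is not always the worst-fitting shape: an over-parameterised model with a good fit can also have the highest AIC.

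The formula belongs to the primary analysis. SAP Section 7 gives a primary objective "to determine an optimal dose candidate for Part 2 by incorporating information of available safety and of efficacy", and the averaged curve is part of that efficacy evidence. A distorted curve could misstate how much effect the lower doses deliver.

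**Working it through.** The SAP gives a formula here and no figure to reproduce, so the check evaluates the formula with each sign.

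**1. Two models (exact).** For an AIC difference D, the lower-AIC model gets 1/(1 + exp(D/2)) as printed and 1/(1 + exp(−D/2)) with the minus sign.

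| D | Printed | Minus sign |
|---|---|---|
| 2 | 0.269 | 0.731 |
| 4 | 0.119 | 0.881 |
| 10 | 0.007 | 0.993 |

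For D = 4: 1/(1 + 7.389) = 0.119 and 1/(1 + 0.135) = 0.881.

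**2. The parameter penalty alone.** The standard forms have p = 2 (linear), 3 (exponential, Emax) and 4 (SigEmax, BetaMod) mean parameters. With equal likelihoods only 2p differs, so the printed weight is proportional to exp(p). For one model each with p = 2, 3 and 4, that is 7.389, 20.086 and 54.598, which sum to 82.07. The weights are 0.090, 0.245 and 0.665. The minus sign gives 0.665, 0.245 and 0.090. Each extra parameter multiplies the printed weight by e = 2.72 instead of 1/e = 0.37.

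**3. Five models fitted to noise-free Emax means (illustration).** The inputs are:
- Placebo change −10% and maximum effect −30 points (Protocol 7.2.3).
- SD 50% (Protocol 7.5, stated for Part 2 only).
- Total doses 0:1:2:4. The linear row of Table 7.4: 2 falls by 0.592 − 0.254 = 0.338, 0.254 + 0.085 = 0.339 and −0.085 + 0.761 = 0.676, assuming equal allocation.
- Group means −10, −29.6, −35.5 and −40, back-calculated from the Emax row.
- An assumed 45 per arm, all five models significant, and AIC = weighted residual sum of squares + 2p.

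| Model | AIC | Printed | Minus sign |
|---|---|---|---|
| Linear | 6.24 | 0.097 | 0.309 |
| Exponential | 8.82 | 0.351 | 0.085 |
| Emax (true) | 6.00 | 0.086 | 0.349 |
| SigEmax | 8.00 | 0.233 | 0.128 |
| BetaMod | 8.00 | 0.233 | 0.128 |

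The true shape gets the least weight and the exponential gets the most.

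**4. Simulation.** The doses, SD and effect size are as in step 3, with 4,000 trials for each true shape and arm size. The five contrasts come from Table 7.4: 2, with a simulated critical value of 2.00 at one-sided 0.05, and the significant models were refitted with bounded parameters. At least two models are significant in 55–74% of trials at 30 per arm and in 96–99% at 100. The table gives the RMSE of the three effects versus placebo among those trials.

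| True shape, sign | 30 | 45 | 60 | 80 | 100 per arm |
|---|---|---|---|---|---|
| Emax, minus | 10.5 | 8.8 | 8.2 | 7.6 | 7.0 |
| Emax, printed | 7.9 | 8.0 | 8.8 | 9.8 | 10.4 |
| BetaMod, minus | 11.8 | 9.6 | 8.3 | 7.4 | 6.9 |
| BetaMod, printed | 9.9 | 9.0 | 9.2 | 10.2 | 11.1 |

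For the other shapes, minus against printed:
- Linear: 5.2 against 4.8 at 100 per arm. The printed sign is slightly better at every size.
- SigEmax: 6.0 against 5.4 at 100. The printed sign is slightly better at every size.
- Exponential: 9.3 against 9.4 at 30 and 5.5 against 6.5 at 100. The printed sign is slightly worse at every size.

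With an Emax truth at 100 per arm, the mean low-dose effect is −17.9 with the minus sign and −7.9 as printed; the true value is −19.6.

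**The case against.** **Transcription and code.** The equation was read from a PDF by a program, and a minus sign may have been lost. It would have to be lost in both exponents, which is less likely but not excluded. The R code may also use the usual sign. Both points stand as limits: the conclusion concerns the printed formula, not what the program does.

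**Conflict with the protocol.** Protocol 7.2.3 later uses best-fitting as a gloss on the statistically significant models, so its stated aim need not mean low AIC. That is fair. The mismatch with the protocol is secondary, and the error rests on the meaning of AIC.

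**Harm is not uniform.** In the simulation the printed sign has the lower RMSE for four of the five true shapes at 30 and 45 per arm, and for linear and SigEmax at every size tried. With arm size not public, the net effect on accuracy is unknown. This stands too, but the SAP offers no rationale for favouring high AIC. Under an Emax or BetaMod truth the printed rule is less accurate at 100 per arm than at 30, whereas the minus sign improves steadily.

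**Limited reach.** Part 1 testing is non-confirmatory (Protocol 7.1). The single-model curves are plotted with MMRM intervals, so a poor average might be noticed. The Part 2 dose also draws on safety and all available data (Protocol 2.1.1), and population PKPD modelling is planned as well (Protocol 3.2). With one significant model the weight is 1 under either sign. The SAP does not say whether weights are recomputed within each bootstrap sample, so the exact effect on the confidence band is open. All of this limits the consequence without making the formula right.

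**Conclusion.** The concern holds. As printed, the formula reverses Akaike weighting exactly: a 4-point AIC advantage earns 12% of the weight instead of 88%, and a 10-point advantage 0.7% instead of 99.3%. These figures need no assumption beyond the ordinary meaning of AIC.

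The averaged curve and its dose-group estimates are affected whenever at least two models are significant. Under the simulation's assumptions that is the majority of trials at 30 per arm and nearly all at 100. The simulated accuracy results depend on an assumed SD, dose spacing, allocation and arm size, and they point in both directions at small arm sizes. They show that the choice of sign can matter materially, not how large the error would be in this trial.

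Because the formula defines a prespecified output of the primary analysis, it must be corrected. Confidence is high for the printed text; the code could not be checked.

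**What to change.** Print the weight as w(M_k) = exp(−0.5·AIC(M_k)) / Σ exp(−0.5·AIC(M_i)), summed over i = 1 to K, where K is the number of significant models. The printed limit reuses k, which also indexes the model being weighted; that is loose notation and can be tidied in the same edit. Add one line defining AIC as −2 log L + 2p, or the generalised form used with the MMRM estimates.

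Check the original SAP page for a lost minus sign, and confirm that the R code in Section 10.3 uses the negative exponent. If text and code differ, reconcile them and document the change. The cost is a one-line SAP correction and a code check; no patients or data are involved.
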